## 1. Protocol Synopsis

### Title of Study:

Effect of injection site on the relative and absolute bioavailability of single dose of LY900014 in healthy subjects.

### Rationale:

In clinical practice, it is recommended that patients rotate insulin injections and may inject insulin at different tissue sites. The actual site of subcutaneous (SC) injection may influence the absorption pharmacokinetics (PK), as well as, the glucodynamic (GD) effect. The primary objective of this study is therefore to compare the bioavailability of insulin lispro following administration of the commercial formulation of LY900014 at 3 different injection sites SC in the abdominal wall, thigh, and deltoid. In addition, the intravenous (IV) administration will serve as the reference to determine the absolute bioavailability of SC injections into the deltoid, thigh or abdomen and GD activity.

### Objectives/Endpoints:

Objectives	Endpoints

Primary
 
To determine the relative bioavailability of insulin lispro from LY900014 after SC injection into the thigh and deltoid compared to the abdomen in healthy subjects.
 
To determine absolute bioavailability of insulin lispro following SC administrations of LY900014 into the thigh, deltoid and abdomen compared to IV administration of LY900014 in healthy subjects.
	
Area under the concentration versus time curve from time zero to infinity (AUC[0-<math>\infty</math>])
 
Percent of the ratio of AUC(0-<math>\infty</math>)

Secondary
 
To evaluate the tolerability of LY900014 in healthy subjects.
 
To evaluate the GD during euglycemic clamp procedure of LY900014 after SC injection into the abdomen, thigh and deltoid and IV in healthy subjects.
	
Adverse events (AEs) and injection-site reactions
 
Total amount of glucose infused (<math>G_{tot}</math>) and maximum glucose infusion rate (<math>R_{max}</math>).

### Summary of Study Design:

Study I8B-MC-ITRT is a single-center, open-label, 4-period, randomized, crossover, up to 10-hour euglycemic clamp study in healthy subjects to compare the insulin lispro PK and GD of LY900014 after SC administration of a 15-U injection at 3 different injection sites and a single IV bolus injection of 15 U. The SC injection sites are the abdomen, thigh, and deltoid. An IV injection into the forearm will be used to assess absolute bioavailability.

### Treatment Arms and Planned Duration for an Individual Subject:

Subjects will be randomly assigned to 1 of 4 treatment sequences; each sequence will have 4 periods. In 3 of the 4 periods, subjects will be administered single SC doses of 15 U of LY900014 at 3 different injection sites, which include the thigh, abdomen and deltoid. One study period will include a single IV dose of 15 U of LY900014.

The study will include a 28-day screening period, followed by 4 study periods. There will be a wash-out period of at least 3 days between each study period. The follow-up visit will take place at least 14 days after the last dose.

**Number of Subjects:**

Up to 28 healthy men and women may be enrolled to target at least 22 subjects complete the study.

**Statistical Analysis:**

The primary statistical analyses for PK will be conducted on those subjects who receive at least 1 dose of study drug and have measurable insulin lispro concentrations. The primary statistical analysis for GD will be conducted on those subjects who complete at least 1 clamp procedure. Supportive analyses will be done on the key parameters for the subjects who complete all treatment periods with evaluable data.

Safety analyses will be conducted for all enrolled subjects, whether or not they complete all protocol requirements. All investigational product and protocol-procedure AEs will be listed, and if the frequency of events allows, safety data will be summarized using descriptive methodology. Safety parameters that will be assessed include safety laboratory parameters and vital signs, as well as evaluation of injection-site reactions. The parameters will be listed and may be summarized using standard descriptive statistics.

Log-transformed  $AUC(0-\infty)$  and maximum observed serum concentration ( $C_{max}$ ) for insulin lispro will be evaluated to estimate geometric least-squares means (LSmeans), ratios of geometric LSmeans between injection sites (deltoid and thigh compared with the abdomen), and their corresponding 90% confidence interval (CI) using the statistical model that includes injection site, period, and sequence as fixed effects, and subject within sequence as a random effect. The primary parameter for the statistical analysis of the relative bioavailability between injection sites will be the  $AUC(0-\infty)$ .

Log-transformed  $R_{max}$  and  $G_{tot}$  will be evaluated to estimate geometric LSmeans, ratios of geometric LSmeans between injection sites (deltoid and thigh compared with the abdomen), and their corresponding 90% CIs using the statistical model that includes injection site, period, and sequence as fixed effects, and subject within sequence as a random effect. For GD parameters that have at least 1 subject with a value equal to zero, a value equal to the smallest non-zero observed GD value for that parameter divided by 2 will be added to all values, and the analysis of the log-transformed data will be performed. In addition, as a sensitivity analysis, a nonparametric analysis will be performed for that parameter.

The PK and GD analyses will also be performed using the subset of the subjects who complete all treatment periods with evaluable data.

The frequency of antibody formation to insulin lispro will be determined. The relationship between the presence (or absence) of antibodies and AEs will be assessed. Likewise, the relationship between the presence of antibodies and the PK parameters and GD response to insulin lispro may be assessed.

## 2. Schedule of Activities

## Study Schedule of Protocol I8B-MC-ITRT

Procedures	Screening	Periods 1, 2, 3, 4			FU/ EDa	Comments
	Up to Day -28	Day -1	Day 1	Day 2		
Informed consent	X					
Admission to CRU		X				
Enrollment			X			Enrollment prior to taking first predose blood sample for the study.
Overnight fast	X	X				Subjects are expected to fast for approximately 8 hours before screening, and at least 8 hours before each dose until the end of the glucose clamp procedure.
Height	X					
Weight	X	X #			X	# Period 1 only
Hip and waist circumference		X #				# Period 1 only
Medical history and physical examination	X					
Medical assessment	X		Predose	X*	X	Medical assessment includes medical review and physical examination, as appropriate. *Prior to discharge from CRU for each period
Vital signs (supine): blood pressure and pulse rate	X		Predose, 1 hour postdose (IV period only), and 10 hours postdose (at the end of clamp procedure)		X	Predose vital signs may be collected up to 3 hours before dosing.
12-Lead ECG	X		Predose and 10 hours postdose (at the end of clamp procedure)		X	Single ECGs will be collected for safety. Predose ECGs may be collected up to 3 hours before dosing.
Clinical laboratory tests	X		Predose of Period 1. For IV period: 1 hour postdose		X	One hour postdose blood samples will be drawn only for the study period when LY900014 is administered intravenously.
Pregnancy test	X	X			X	For females of childbearing potential only. A serum pregnancy test will be performed at screening and urine pregnancy tests will be performed at all other time points.

Procedures	Screening	Periods 1, 2, 3, 4			FU/ EDA	Comments
		Up to Day -28	Day -1	Day 1		
Study drug administration				0 hour		Time of study drug administration = 0 hour. Study drug will be administered at approximately the same time on Day 1 of each study period. The site of administration will be determined by the randomization schedule.
Injection-site assessments				0, 1, 4, and 10 hours postdose		Time 0: assessments will occur immediately following the injection.
Insulin lispro PK sampling				2.5, 5, 10, 15, 20, 25, 30, 40, 60, 70, 90, 120, 150, 180, 210, 240, 300, 360, 420, 480, 540, and 600 minutes		Sampling times are relative to the time of study drug administration (time 0).
Treprostinil PK sampling (IV period only)				2.5, 5, 10, and 30 minutes		Only for the study period when LY900014 is administered intravenously. Sampling times are relative to the time of study drug administration (time 0).
C-peptide samples				0, 30, 60, 120, 180, 240, 300, 360, 420, 480, 540, and 600 minutes		Sampling times are relative to the time of study drug administration (time 0).
Blood glucose sampling for euglycemic clamp				Approximately every 10 minutes for approximately 30 minutes before the start of dosing (for baseline measurement). During clamp, sampling occurs every 2.5 minutes for the first 30 minutes; every 5 minutes for 30 to 120 minutes; every 10 minutes for 120 to 480 minutes and every 20 minutes for 480 to 600 minutes.		Sampling times are relative to study drug administration (time 0). Glucose samples should be taken before PK samples. Failure to obtain samples due to clinical issues, such as problems with venous access, will not be considered a protocol violation. Repeat samples for counter-checking of apparent spurious results may be taken where indicated.
Pharmacogenetic sample		X				Period 1 only.
Immunogenicity sample				Predose of Periods 1 and 3	X	Additional samples may be collected if the investigator considers there is a possibility that an adverse event is immunologically indicated.
Discharge from CRU					X	Subjects will be discharged on Day 2.

Abbreviations: CRU = clinical research unit; ECG = electrocardiogram; ED = early discontinuation; FU = follow-up; IV = intravenous; PK = pharmacokinetics.

a Procedures should be performed at least 14 days after the last dose of study drug.

Note: The site should schedule activities as appropriate. In cases when several study procedures are scheduled at the same time, the order of priority will be as follows: glucose samples, PK samples, injection-site assessments, vital signs, ECG, clinical laboratory samples. If the investigator decides based on clinical judgment not to dose a subject on a given day (eg, because of low blood glucose), the subject's visit may be rescheduled; any procedures performed in that period may be repeated.

### 3. Introduction

#### 3.1. Study Rationale

In clinical practice, it is recommended that patients rotate insulin injections and may inject insulin at different tissue sites. The actual site of subcutaneous (SC) injection may influence the absorption pharmacokinetics (PK), as well as, the glucodynamic (GD) effect. The primary objective of this study is therefore to compare the bioavailability of insulin lispro following administration of the commercial formulation of LY900014 at 3 different injection sites SC in the abdominal wall, thigh, and deltoid. In addition, the intravenous (IV) administration will serve as the reference to determine the absolute bioavailability of SC injections into the deltoid, thigh, or abdomen and GD activity.

#### 3.2. Background

The insulin analog, insulin lispro (Humalog®), has been shown to be absorbed more quickly than regular human insulin (Humalog package insert, 2015). In healthy volunteers given SC doses of insulin lispro ranging from 0.1 to 0.4 U/kg, peak serum levels were seen 30 to 90 minutes after dosing (Humalog package insert, 2015). However, the general consensus is that rapid-acting insulin, administered either through pumps or syringes/pen injectors, is still not rapid enough to match carbohydrate absorption profiles, which limits efficacy and dosing flexibility. An ultra-rapid-acting prandial insulin would shift the PK and GD profiles so that they have an even faster onset to better match carbohydrate absorption.

LY900014 is an ultra-rapid-acting insulin lispro formulation with treprostinil (active ingredient in Remodulin®) and other ingredients. LY900014 has an increased early absorption of insulin lispro compared to commercially available insulin lispro (Humalog; Eli Lilly and Company). This formulation involves the novel use of a microdose of treprostinil as an excipient to enhance the absorption of insulin lispro through local vasodilatation rather than as an active pharmaceutical ingredient to elicit a systemic effect.

Treprostinil is a prostacyclin analog, administered either through inhalation (Tyvaso®), as an IV infusion, or as a continuous SC administration for the treatment of symptomatic pulmonary arterial hypertension (PAH) and has been approved in the US since 2002 (Remodulin package insert, 2014). Each of the other excipients (such as sodium citrate and magnesium chloride) in the LY900014 formulation is listed in the US Food and Drug Administration (FDA)'s Generally Recognized as Safe Food Additives database and in the FDA's Inactive Ingredients in Approved Drugs database. Furthermore, the excipient concentration in LY900014 is within the limits identified for approved drug products in the FDA Inactive Ingredients in Approved Drugs database.

Safety and tolerability of LY900014 have been demonstrated in healthy subjects in 3 previous clinical studies, in approximately 71 healthy subjects across a dose range of 7.5 to 30 U. All 4 studies were Phase 1, randomized, subject-blind studies in which the PK and GD of LY900014 and Humalog were evaluated during a euglycemic glucose clamp following SC administration. The total insulin lispro exposure and GD effect were similar for LY900014 and Humalog;

however, LY900014 demonstrated a faster and earlier insulin lispro absorption compared to Humalog.

In addition, data from two Phase 1b studies showed LY900014 was well tolerated in patients with type 1 diabetes mellitus (T1DM; 30 patients) and type 2 diabetes mellitus (T2DM; 30 patients) using multiple daily injections (MDIs). There were no serious adverse events (SAEs) related to study treatment or discontinuations from the studies because of a drug-related adverse event (AE). Small numbers of treatment-emergent adverse events (TEAEs) were reported, and there were no notable increases in these events in relation to any of the LY900014 formulations compared to those in relation to Humalog.

More information can be found in the Investigator's Brochure (IB) of LY900014.

### **3.3. Benefit–Risk Assessment**

Study I8B-MC-ITRT (ITRT) will not offer any direct benefits to the subjects participating in the study. The data from previous studies in healthy subjects and data from studies in patients with T1DM and T2DM have shown that LY900014 was well tolerated and the adverse drug reactions are in keeping with those reported for Humalog.

Potential risks associated with LY900014, derived from the known risks of insulin lispro (Humalog), are hypoglycemia, hypersensitivity reactions (localized allergy and/or systemic allergy), undesirable effects at the injection site (injection-site reactions and lipodystrophy), and peripheral edema (Humalog package insert, 2015).

Notably, across all doses in the Lilly clinical studies that have evaluated treprostinil as a local vasodilator with or without insulin lispro, there was no clinically significant increase in those AEs associated with systemic absorption of treprostinil, as described in the Remodulin package insert (2014). The exposures of treprostinil in LY900014 in this study are expected to be undetectable compared to those observed in the dose ranges previously explored with SC bolus administration of treprostinil and are expected to be substantially lower than those observed in the treatment of PAH.

In preclinical safety pharmacology and toxicity studies, or clinical pharmacology studies involving LY900014 or treprostinil alone, other than known risks associated with Humalog and Remodulin, no additional risks were identified. No known potential risks are associated with the use of small amounts of treprostinil (Remodulin) in the LY900014 formulation.

Additionally, local and systemic toxicity profiles of Humalog and Remodulin do not suggest the potential for additive or synergistic toxicity.

Following administration of the study insulin, subjects will receive IV glucose infusion at a variable rate to maintain euglycemia up to 10 hours after insulin lispro administration. The aim of the clamp procedure is to maintain blood glucose within the normal glycemic range. In addition, the clamp is performed while the subject is inpatient and under the investigator's supervision. These considerations should minimize the risk of hypoglycemia in subjects participating in Study ITRT.

More information about the known and expected benefits, risks, SAEs, and reasonably anticipated AEs of LY900014 are to be found in the IB.

## 4. Objectives and Endpoints

Table ITRT.1 shows the objectives and endpoints of the study.

**Table ITRT.1. Objectives and Endpoints**

Objectives	Endpoints
Primary To determine the relative bioavailability of insulin lispro from LY900014 after SC injection into the thigh and deltoid compared to the abdomen in healthy subjects.	AUC(0-∞)
To determine absolute bioavailability of insulin lispro following SC administrations of LY900014 into the thigh, deltoid, and abdomen compared to IV administration of LY900014 in healthy subjects.	Percent of the ratio of AUC(0-∞)
Secondary To evaluate the tolerability of LY900014 in healthy subjects.	Adverse events and injection-site reactions
To evaluate the GD during euglycemic clamp procedure of LY900014 after SC injection into the abdomen, thigh, and deltoid and IV in healthy subjects.	$G_{tot}$ and $R_{max}$
Exploratory Objectives To evaluate C-peptide levels after administration of LY900014.	C-peptide concentrations
To determine plasma concentrations of the excipient, treprostinil, following administration of a single, IV 15-U dose of LY900014 in healthy subjects.	Plasma concentrations–over-time profile

Abbreviations: AUC(0-∞) = area under the concentration versus time curve from time zero to infinity; GD = glucodynamics;  $G_{tot}$  = total amount of glucose infused; IV = intravenous;  $R_{max}$  = maximum glucose infusion rate; SC = subcutaneous.

## 5. Study Design

### 5.1. Overall Design

This is a Phase 1, single-center, open-label, 4-period, randomized, crossover, up to 10-hour euglycemic clamp study in approximately 28 healthy subjects to compare the insulin lispro PK and GD of LY900014 after SC administration of a 15-U dose at 3 different injection sites and a single IV bolus injection of 15 U. The SC injection sites are the abdomen, thigh, and deltoid.

Subjects will be required to attend the clinical research unit (CRU) on at least 6 occasions:

[figure not shown]
- screening visit (may occur up to 28 days before randomization)
- four treatment visits for the clamp procedure (study Periods 1 to 4) with a wash-out period of  $\geq 3$  days between discharge and the next admission to the CRU
- follow-up visit (at least 14 days after last dose), or early discontinuation.

Each subject will be randomly assigned to a treatment sequence and will be administered single doses of 15 U of LY900014 (on 4 occasions).

Subjects will be admitted to the CRU on the evening before each dosing day and will remain in the CRU for the duration of the clamp period and until discharge by the investigator. Subjects are expected to fast for at least 8 hours before each dose. Following dose administration, each subject will undergo an euglycemic clamp procedure of up to 10 hours. Upon completion of the clamp procedures, the subjects will be provided a meal and observed overnight. Subjects will be discharged from the CRU the next day after medical assessments.

Study governance considerations are described in detail in [Appendix 3](#).

[Figure ITRT.1](#) illustrates the study design and [Table ITRT.2](#) presents the treatment sequences.

Abbreviations: CRU = clinical research unit; IV = intravenous; SC = subcutaneous.

\*Single dose of LY900014 administered either SC in the abdomen, thigh, deltoid or IV. Up to 10-hour euglycemic clamp procedure after each dose.

**Figure ITRT.1.**

**Illustration of study design of Protocol I8B-MC-ITRT.**

**Table ITRT.2.**

**LY900014 Treatment Sequences**

Treatment Sequence	Period 1	Period 2	Period 3	Period 4
1	LY900014 Abdomen	LY900014 Thigh	LY900014 Deltoid	LY900014 IV
2	LY900014 Deltoid	LY900014 Abdomen	LY900014 IV	LY900014 Thigh
3	LY900014 IV	LY900014 Deltoid	LY900014 Thigh	LY900014 Abdomen
4	LY900014 Thigh	LY900014 IV	LY900014 Abdomen	LY900014 Deltoid

Abbreviation: IV = intravenous.

Note: Subcutaneous injection sites are the abdomen, deltoid and thigh.

## 5.2. Number of Participants

A total of 28 subjects may be enrolled so that at least 22 subjects complete the study. For purposes of this study, a subject completes the study when all scheduled procedures shown in the Schedule of Activities (Section 2) have been completed.

If subjects discontinue from the study before completion of all 4 study periods, replacement subjects may be enrolled up to 28 subjects following agreement between the investigator and the sponsor.

A replacement subject will be assigned the treatment sequence of the discontinued subject and complete that treatment sequence in its entirety.

## 5.3. End of Study Definition

End of the study is the date of the last visit or last scheduled procedure shown in the Schedule of Activities (Section 2) for the last subject.

#### 5.4. Scientific Rationale for Study Design

A population of healthy subjects is selected based on the likelihood of less physiologic variability in the absence of disease states that may affect multiple organ systems and absence of other confounding factors such as concomitant medications.

The use of a crossover design allows each subject to serve as his or her own control, thereby reducing variability.

A euglycemic clamp technique, the gold standard methodology for assessing insulin action, will be used in this study to provide data on the GD activity of LY900014 (see Section 9.6 for a detailed description of the clamp methodology). Based on previous studies, the 10-hour duration of the euglycemic glucose clamp will allow for a complete assessment of GD activity of LY900014.

Based on the PK properties of treprostinil (half-life associated with the terminal rate constant in noncompartmental analysis [ $t_{1/2}$ ] = approximately 1 hour) and Humalog ( $t_{1/2} = 0.79$  hours), the duration of the washout period between clamp visits (a minimum of 3 days) and the duration between the last dose of study drug and the follow-up visit (at least 14 days) are considered appropriate.

#### 5.5. Justification for Dose

Based on previous studies of both insulin lispro (Humalog) and LY900014, the 15-U dose is within the clinical dose range and should provide measurable PK and GD profiles for insulin lispro. The insulin lispro concentrations in the body resulting from administration of this dose to healthy subjects are anticipated to be measurable over the sampling period. Additionally, it is anticipated that this dose will provide an adequate glucose infusion rate (GIR) for assessment of GD.

The safety, PK, and pharmacology of LY900014 at similar doses and with the similar formulation composition have been assessed in clinical studies in healthy subjects, in patients with T1DM using MDI or insulin pump treatment and T2DM using MDI. In addition, the components of LY900014 have been tested in 3 clinical studies that included the evaluation of the safety, PK, and pharmacology of SC bolus doses of treprostinil (see LY900014 IB).

All tested doses of treprostinil (CCI [REDACTED]), insulin lispro, and LY900014 were well tolerated in healthy subjects, patients with T1DM, and patients with T2DM. There were no SAEs related to study treatment in any of the 8 studies. No subject discontinued from the studies because of drug-related AEs. Trial participants in these studies were monitored for changes in vital signs; there were no significant systemic hemodynamic effects of treprostinil at the doses administered based on blood pressure and heart rate. Visual analog scale pain scores showed that the SC injections of insulin lispro plus treprostinil co-formulations and treprostinil alone were well tolerated.

In summary, there were small numbers of TEAEs and injection-site AEs, but there was no clinically significant increase in these or other events compared to placebo or to Humalog and no

clinically significant increase in frequency with higher doses of treprostinil. Notably, at the higher doses of treprostinil, there was no clinically significant increase in those AEs associated with systemic absorption as described in the Remodulin package insert (2014) (that is, headache, diarrhea, nausea, jaw pain, vasodilatation, rash, edema, and hypotension). This is likely attributable to the relatively lower exposures of treprostinil demonstrated in these clinical studies.

It is expected that the treprostinil concentration in the plasma following the 15-U IV bolus administration of LY900014 containing **CCI** of treprostinil to be below the lower limit of quantitation (LLOQ). As published, the SC infusion of Remodulin has a 100% absolute bioavailability (Remodulin package insert, 2014); thus, it is expected that plasma exposures of treprostinil between IV and SC administrations of LY900014 will be similar. The PK of treprostinil in LY900014 following SC administration of 15 U of LY900014 was assessed in previous studies. In these studies, treprostinil exposure was not detectable for the 15-U dose of LY900014.

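### Does 100% SC bioavailability justify expecting undetectable treprostinil after the IV bolus, and do the IV-period vital signs come too late?

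*Protocol*

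**What the plan says.** Protocol section 5.5 gives two grounds for expecting treprostinil to stay below the lower limit of quantitation (LLOQ) after the IV dose. The first is the published 100% absolute bioavailability of subcutaneous (SC) treprostinil infusion: "thus, it is expected that plasma exposures of treprostinil between IV and SC administrations of LY900014 will be similar". The second is earlier SC experience, in which "treprostinil exposure was not detectable for the 15-U dose of LY900014".

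On safety, the same section says that in earlier studies "there were no significant systemic hemodynamic effects of treprostinil at the doses administered based on blood pressure and heart rate". It describes the studies of the formulation's components as including "evaluation of the safety, PK, and pharmacology of SC bolus doses of treprostinil".

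In the Schedule of Activities (Protocol section 2), treprostinil is sampled in the IV period only, at "2.5, 5, 10, and 30 minutes". Vital signs are due "Predose, 1 hour postdose (IV period only), and 10 hours postdose (at the end of clamp procedure"). Section 9.4.2 adds orthostatic readings when symptoms occur, and further readings if warranted. Protocol section 10.3.2.1 and SAP section 9.3.1 focus the treprostinil analysis on Cmax and tmax. Table ITRT.1 lists treprostinil as exploratory, and section 10.3.4 plans no PK/PD analysis.

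**The concern.** Bioavailability determines total exposure. Whether a sample is detectable depends on the concentration when it is drawn. An IV bolus has no absorption phase, so its peak is higher than that of an SC dose with the same area. The SC non-detection result carries over to the IV case only through the claim of similar exposure, so the below-LLOQ expectation does not follow from the reasons given.

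The timing looks like a second weakness. Treprostinil sampling covers the first 30 minutes after the bolus, yet no scheduled postdose blood pressure or pulse falls there. If treprostinil had a brief haemodynamic effect near its peak, scheduled readings could miss it. The 1-hour reading belongs to the IV period alone, so the by-treatment summary in SAP section 9.5.4 can compare IV with SC after dosing only at 10 hours.

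**Working it through.** The documents state no figure for the IV peak, so there is none to reproduce.

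**Inputs.** The treprostinil half-life is about 60 minutes (Protocol section 5.4). Bioavailability is F = 1 (section 5.5). IV dosing is a bolus push (section 7.2.1). The SC absorption half-life is not documented; 5, 15, 30 and 60 minutes are assumed.

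**One-compartment model**, with concentrations relative to the initial IV value C0:
- IV: C(t) = exp(−ke·t), with ke = ln2/60 per minute.
- SC: tmax = ln(ka/ke)/(ka − ke), or 1/ke when ka = ke; peak = exp(−ke·tmax).
- Area: dose/clearance for both routes, so the AUC ratio is 1.00.
- IV at 2.5 minutes: 2^(−2.5/60) = 0.972.

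| SC absorption half-life (min) | SC tmax (min) | SC peak / C0 | IV peak / SC peak | Largest SC peak, as share of LLOQ, that keeps the 2.5-min IV sample below LLOQ |
|---|---|---|---|---|
| 5 | 19.6 | 0.798 | 1.25 | 0.798/0.972 = 82% |
| 15 | 40.0 | 0.630 | 1.59 | 65% |
| 30 | 60.0 | 0.500 | 2.00 | 51% |
| 60 | 86.6 | 0.368 | 2.72 | 38% |

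**Sensitivity.**
- Assuming SC tmax of 5 to 60 minutes instead gives peak ratios of 1.06 to 2.00.
- Reading the half-life as 45 to 75 minutes gives 1.21 to 3.16.
- An assumed distribution phase (50% to 90% of C0, half-life 3 to 10 minutes, SC absorption half-life 10 to 30 minutes, terminal half-life 1 hour) gives about 2.4 to 10.5 for the peak and 2.0 to 6.4 for the 2.5-minute sample. One numerically singular combination is left out.

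The direction is the same throughout; the size depends on the assumptions.

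**Timing.** The gap is 60 − 30 = 30 minutes. In one compartment, 71% of C0 remains at 30 minutes, 50% at 60 minutes and 2^(−10) = 0.1% at 10 hours. The 1-hour IV level is then 0.500/0.798 = 63% to 0.500/0.368 = 136% of the SC peak. With the distribution phase it is about 0.068 × 2.68 = 18% to 0.326 × 2.90 = 95%. The 1-hour reading is therefore taken while drug remains, though after the peak.

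**Do the texts conflict?** Section 5.5 states an expectation. The treprostinil row times an exploratory assay, and the vital-signs row times a safety measure. Nothing says that the two rows should coincide, so there is no contradiction to reconcile.

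**Would a change help?** The early samples and the Cmax focus already test the expectation, whatever section 5.5 says. Earlier IV-period readings would have no SC readings at the same times, so the comparison with SC would stay at 10 hours. Table ITRT.2 has no IV arm of insulin lispro alone, so an early change could not be attributed to treprostinil rather than to the rest of the bolus.

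**The case for a change.** The strongest case for acting is that the error in reasoning is plain and cheap to correct. Section 5.5 states no margin below the LLOQ, and an assay result cannot supply a blood pressure that was never taken. The earlier haemodynamic data come from SC dosing, and the redacted dose range prevents a check that they reach an IV peak.

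The criticism of the reasoning stands, and so does the observation that no scheduled reading covers the peak. Neither shows a fault that changes the trial. Section 3.2 reports tolerability of SC LY900014 at 7.5 to 30 U in about 71 healthy subjects. If treprostinil content per unit was constant (an assumption), 30 U SC gives twice the 15-U SC peak. That covers one-compartment ratios up to 2.00, but not 2.72 or the distribution-phase values, so this support is partial. Section 5.5 also reports no clinically significant increase in systemic adverse events, hypotension among them, at the higher treprostinil doses.

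Subjects are supervised inpatients (section 3.3), recumbent or sitting (section 6.3.3), with resuscitation equipment available at dosing (section 7.1). Glucose is drawn every 2.5 minutes in the first half hour, and when procedures coincide "the order of priority will be as follows: glucose samples, PK samples, injection-site assessments, vital signs, ECG, clinical laboratory samples". How to use that crowded window is a clinical scheduling judgement.

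**Conclusion.** The inference in section 5.5 is looser than its wording suggests: F = 1 supports similar AUC, while the IV peak is about 1.1 to 2.7 times the SC peak in the one-compartment model, and higher if there is a distribution phase. These factors rest on assumed SC absorption, linear kinetics and the stated 1-hour half-life. With the treprostinil dose redacted and the LLOQ not given, the expectation can be neither confirmed nor refuted.

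No change follows. Reading exposure in section 5.5 as AUC closes the gap, and the planned 2.5 to 30 minute samples settle the peak. The 30-minute interval before the first scheduled postdose vital signs is a design choice that conflicts with no other text. It affects only descriptive safety data, and moving the IV-period readings would give neither a matched SC comparison nor a treprostinil-specific one. The primary bioavailability analyses are untouched.
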